2.4.3 Primary analysis

The primary efficacy endpoint will be a responder rate based on the subject GAIS at maximum frown at Month 1 (described in [Section 1.4.1](#)). To evaluate the effectiveness and superiority in aesthetic improvement of QM1114-DP versus placebo in the treatment of moderate to severe GL, the responder rates of QM1114-DP and placebo will be compared using a Cochran-Mantel-Haenszel (CMH) test stratified by site at the 5% significance level (2-sided). The primary efficacy endpoint will be based on the ITT population where missing Month 1 GAIS data will be imputed with 'No Change'.

The null hypothesis of no relationship between treatment and responder rate (i.e., the responder rates are the same in both groups) will be tested against the alternative hypothesis that there is a relationship between treatment and responder rate (i.e., the responder rates are different in the two groups). For a significant result, the two-sided p-value of the comparison of the GAIS responder rate between the QM1114-DP and placebo subjects at Month 1 using the CMH test needs to be smaller than 0.05. For consistency across strata (site), the Breslow-Day test will be used to assess the homogeneity of odds ratios across all sites. If the Breslow-Day test is significant, then the responder rates between the QM1114-DP and Placebo treatment groups will be presented by site.

The estimates of the GAIS responder rates in each treatment group will be presented as well as the difference in responder rates (QM1114-DP responder rate – placebo responder rate). Corresponding 95% CI for the treatment group GAIS responder rates and the difference in responder rates along with the p-value for the difference will also be presented. The normal approximation (Wald) method will be used to calculate both the 95% CI for the individual treatment group GAIS responder rates and the 95% CI for the difference in responder rates. The above responder rates will be presented in figures by visit and treatment group.

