5. SELECTION AND DISPOSITION OF CLINICAL STUDY POPULATION

5.1 Number of Subjects

As a screen failure rate of approximately 10% is anticipated, approximately 134 subjects will be screened in order to get 120 subjects enrolled in a 3:1 ratio to QM1114-DP 50 U (N=90) or placebo (N=30). It is expected that each center will recruit a similar number of subjects.

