6.1.5 Method of Treatment Assignment

Before starting the study, a randomization list stratified by study center will be generated. When the investigator has confirmed subject eligibility, the subject will be allocated a study product within the electronic data capture (EDC) system.

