2.1 General methods

All tables, listings, and figures will be programmed using SAS Version 9.4 or higher. Data collected in this study will be documented using summary tables and subject data listings created by the SAS® system. Confidence intervals (CI) and p-values will be 2-sided and performed at a significance level of 5%, unless otherwise specified. Data for all subjects in the clinical database will be included in the data listings. Calculated (derived) variables will be listed as appropriate. Any changes from the SAP will be detailed in the clinical study report.

All efficacy, safety and baseline characteristics variables will be presented using descriptive statistics within each treatment group, and graphs as appropriate. Continuous variables will be summarized using descriptive statistics (n [number of observations], mean, standard deviation [SD], median, minimum, and maximum), unless otherwise specified. Categorical variables will be presented in frequency tables with number and percentage of observations for each level.

Study days will be calculated relative to the injection of study drug. Day 0 will be the day of study drug administration. Baseline will be the last assessment prior to the injection of study drug unless otherwise indicated. The Screening Visit 1 (Day -14 to Day 0) will be considered the visit prior to injection of study drug. Because the Screening visit and Baseline visit (Day 0) may be performed on the same day, the Screening visit can also be Day 0.

Adverse events, cosmetic/aesthetic procedures and implant history events, medical history events, previous neuromodulator treatments, and concomitant treatments/procedures will be coded using MedDRA, Version 25.0 or higher. Prior/concomitant medications and procedural anesthetics will be coded using the World Health Organization (WHO) Drug Dictionary Global, March 2022 B3 or higher.

In general, efficacy, safety, and exploratory analyses will be performed and summarized by treatment group (QM1114-DP, placebo), unless otherwise stated.

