2. Then, a second SAS PROC MI procedure will be used for imputing missing values of data with monotone missing pattern. Imputations will be made using the MCMC-imputed dataset from step one (1). A linear regression will be employed to model the missing GAIS scores with the following covariates included in each imputation model: treatment group and all non-missing GAIS scores from earlier scheduled time points, including baseline. The seed number to be used will be the number 110196 and five (5) sets of imputations will be created. The Month 1 GAIS responder variable will be calculated from the imputed GAIS values as detailed in [Section 1.3.1](#).
3. The imputed datasets will be analyzed as specified in [Section 2.4.3](#).
4. The results from the CMH analysis of the multiple imputed datasets will be combined using the Wilson-Hilferty transformation by Ratitch et al. [1] to produce a pooled CMH statistic and p-value. The differences in proportions and standard errors will be combined using the SAS PROC MIANALYZE. The resulting pooled difference and standard error will be used to produce the 95% CI based on the large-sample approximation method for binary data without using continuity correction.

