2.4.5.3 GAIS

The GAIS aesthetic improvement (overall appearance) as determined by the subject at all applicable post-treatment time points will be a responder rate based on the subject GAIS at maximum frown at Month 1 (described in [Section 1.3.1](#)). The responder rate will be presented separately by treatment group by visit. The 95% CIs around the estimates will also be provided. The normal approximation (Wald) method will be used to calculate the 95% CIs. The actual GAIS ratings of the subject will also be presented similarly by treatment group and visit. A graph will be provided showing the responder rates over time.

CCI

CCI

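### Wald 95% intervals with 30 placebo subjects and no rule for boundary counts: reported precision can be too optimistic, chiefly for low placebo rates, the treatment difference and small subgroups

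*SAP*

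**What the plan says.** SAP 2.4.3 (Primary analysis): "The normal approximation (Wald) method will be used to calculate both the 95% CI for the individual treatment group GAIS responder rates" and, in the same sentence, "the 95% CI for the difference in responder rates". No continuity correction, boundary rule or fallback is given.

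SAP 2.4.5.3 (GAIS by visit): "The normal approximation (Wald) method will be used to calculate the 95% CIs".

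SAP 2.4.4.2 (Subgroup analysis) repeats the 2.4.3 analysis and asks for rates, differences and 95% intervals in each subgroup. One subgroup variable, prior botulinum toxin use, has five categories.

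SAP 2.4.2, step 4 (multiple imputation sensitivity analysis) uses a "95% CI based on the large-sample approximation method for binary data without using continuity correction".

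SAP 2.1 sets all intervals two-sided at the 5% level, so nominal coverage is 95%. Protocol 5.1 plans 90 active and 30 placebo subjects. Protocol 6.1.5 says that "a randomization list stratified by study center will be generated", and the primary CMH test is stratified by site. No stratum weighting is described for the difference or its interval.

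The expected responder rates (Protocol 9.2.1 to 9.2.3) are redacted.

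**The concern.** SAP 2.4.4 makes the difference in responder proportions the primary estimand, so its 95% interval is the trial's main statement of precision. The Wald interval estimates its standard error from the observed proportion. As that proportion nears 0 or 1 the standard error shrinks towards zero, and with 30 subjects this happens at counts that can plausibly occur. The interval is then too short, can run past 0% or 100%, or collapses to a point. In the difference, a placebo count of zero removes the placebo arm's contribution to the variance altogether. At stake is how far a reader can trust the stated error bars for the primary difference, the by-visit rates and, above all, the small subgroups.

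**Working it through.** **Inputs.** n = 90 and 30 (Protocol 5.1; 3:1 of 120 gives 90 and 30). z = 1.96 (SAP 2.1). The plan's sample-size calculation cannot be reproduced because its rates and power are redacted. All true rates below are assumptions: placebo up to 30%, active 80% to 99%.

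**Formulas.**
- Wald, one rate: p̂ ± z√(p̂(1−p̂)/n).
- Wald, difference: d ± z√(p̂₁(1−p̂₁)/n₁ + p̂₀(1−p̂₀)/n₀).
- Newcombe, with Wilson limits (l, u) for each arm: lower = d − √((p̂₁−l₁)² + (u₀−p̂₀)²); upper = d + √((u₁−p̂₁)² + (p̂₀−l₀)²).
- Exact coverage at true rate p: the sum of the binomial probabilities of all counts whose interval contains p. For the difference, the sum runs over both arms' counts jointly.

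**Worked cases.**
- 0/30: the Wald standard error is 0, so the interval is 0% to 0%. The Wilson upper limit is z²/(n+z²) = 3.84/33.84 = 11.4%; Clopper-Pearson gives 11.6%.
- 1/30: Wald 3.3% ± 6.4%, i.e. −3.1% to 9.8%; Wilson 0.6% to 16.7%.
- 88/90 versus 0/30: d = 97.8%, Wald standard error √(0.978×0.022/90 + 0) = 1.55%, interval 94.7% to 100.8%. Newcombe lower limit: 0.978 − √((0.978−0.923)² + (0.114−0)²) = 85.2%; upper limit 99.4%.

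**Coverage of the difference, 90 versus 30.**

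| Active/placebo | Wald | Newcombe | Wald upper limit above 100% |
|---|---|---|---|
| 80/30 | 93.2% | 94.9% | 0% |
| 80/20 | 93.0% | 94.6% | 0% |
| 90/15 | 91.3% | 95.2% | 0.1% |
| 90/10 | 91.0% | 94.9% | 0.4% |
| 95/5 | 87.8% | 94.0% | 23% |
| 98/3 | 81.4% | 94.1% | 76% |

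Newcombe is not perfect at the extremes: 92.5% at 99/1, where Wald gives 70.0%, and 91.2% at 98/1, where Wald gives 87.9%.

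**Coverage of the placebo rate, n = 30.**

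| True rate | Wald | Wilson | Chance of 0/30 |
|---|---|---|---|
| 5% | 78.2% | 93.9% | 21% |
| 10% | 80.9% | 97.4% | 4% |
| 15% | 94.2% | 96.5% | 0.8% |
| 20% | 94.6% | 96.4% | 0.1% |
| 30% | 95.3% | 93.0% | about 0% |

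**Coverage of the active rate, n = 90.** Wald gives 92.4–94.7% at 80, 85, 90, 93, 95 and 97%, with a dip to 87.6% at 96%. It falls to 83.5% at 98% and 59.5% at 99%.

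**Subgroups.** Five prior-toxin categories, if evenly filled and not overlapping, hold 30/5 = 6 placebo and 90/5 = 18 active subjects each. At n = 6, Wald coverage is 61.7% at 15%, 72.1% at 20% and 87.1% at 30%, with zero-width intervals in 38%, 26% and 12% of cases. Wilson covers 95–99%. For 18 versus 6 at 90/20, the difference is covered 79% of the time by Wald and 96% by Newcombe.

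**Site strata.** With exactly 3:1 in each site, the Mantel-Haenszel weight n₁n₀/(n₁+n₀) equals 0.75n₀. It is therefore proportional to site size, and the weighted difference equals the crude one. Simulation (200,000 trials, five sites of 18:6) compared the crude Wald interval with a Mantel-Haenszel-weighted stratified one:
- Equal site rates at 95/5: coverage 87.7% crude and 87.3% stratified; mean width 0.169 and 0.159.
- Site rates varying (active 70–98%, placebo 5–40%): coverage 94.3% crude and 91.5% stratified; mean width 0.318 and 0.283.

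**The case against.** The strongest reply is that the damage depends on rates nobody outside the sponsor can see. A reader might infer that placebo response is expected near 0% and active response near 100%. The readable text does not say so. Protocol 1.3 says only that placebo subjects are not expected to benefit clinically. The endpoint is self-rated and a single step of improvement counts as response, so placebo rates of 15–30% are quite possible, and there the full-arm placebo interval performs well. Counting missing Month 1 ratings as 'No Change' also keeps the active rate away from 100%. This stands, and it is why the sizes are given as a range. It does not rescue the difference, which covers about 91–94% at 80–95% active against 15–30% placebo, nor the small subgroups.

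A reader might also infer that ignoring site makes the interval too narrow. The calculation shows otherwise: the crude interval is slightly wider than the stratified Wald interval and covers no worse. What remains is that the interval and the stratified test do not match in form.

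Finally, success is decided by the CMH p-value, and Protocol 9.1.5 makes the other efficacy endpoints descriptive. This also stands. Over 80–98% active and 3–30% placebo, the chance that the Wald lower limit reaches zero is at most about 0.1%. A zero-width interval for the difference needs both 90/90 and 0/30, which has a chance of about 0.2% at 95/5.

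**Conclusion.** The concern holds as a should-fix point on reported precision. The Wald interval for the primary difference falls modestly short of 95% at moderate rates (91–93% at 80–90% active against 10–30% placebo) and clearly short when both rates are extreme (88% at 95/5, 81% at 98/3). The placebo arm's own interval is poor if the true rate is about 10% or lower and adequate at 15–30%. The active arm's interval fails badly only from about 98%. Subgroups with about 6 placebo subjects are poorly served even at moderate placebo rates.

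These sizes rest on assumed rates, the planned 90/30 split and, for subgroups, an even spread over five categories. The documents do not support reading this as a threat to the primary test, or as an error caused by leaving site out of the interval.

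**What to change.** In SAP 2.4.3, 2.4.4.2 and 2.4.5.3, replace the Wald method with Wilson or Clopper-Pearson intervals for single responder rates and Newcombe or Miettinen-Nurminen intervals for differences. These handle counts of zero and 100% without a separate rule.

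Optionally, use a site-stratified version for the primary difference so that its form matches the CMH test. The reason is coherence only. The coverage of a stratified Newcombe or Miettinen-Nurminen interval was not computed here.

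The pooled interval after multiple imputation in 2.4.2 is also a large-sample one. It belongs to a sensitivity analysis and is not part of this change, but the SAP could note that it shares the limitation at extreme rates.

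The cost is SAP wording before database lock and usually somewhat wider intervals. These are standard PROC FREQ options. Trial conduct, sample size and the primary test do not change.

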2.4.4 Primary Efficacy Estimand

The primary estimand is the treatment difference between QM1114-DP and placebo in proportion of subjects that have at least “Improved” from baseline; the number of subjects that select “Improved”, “Much Improved”, or “Very Much Improved” on the GAIS at Month 1, divided by the number of subjects that completed the GAIS at Month 1, in all randomized subjects (ITT population).:

Primary Endpoint	Estimand	
Responder rate in aesthetic improvement at Month 1 as assessed by the subject using the GAIS		Population: all randomized subjects (ITT population)
Endpoint: the number of subjects that select “Improved”, “Much Improved”, or “Very Much Improved” on the GAIS at Month 1, divided by the number of subjects that completed the GAIS at Month 1		
	Intercurrent Events: 
 1. Missing Month 1 observation 2. Administered treatment not according to randomization 3. Use of prohibited treatment/procedure in or near the treatment area between 9 months prior to study treatment and Month 1 after study treatment 4. History or presence of eyelid or eyebrow ptosis at Baseline 	Handling of intercurrent events: 
 1. Impute using the result of ‘No Change’ 2. Use observed response 3. Use observed response 4. Use observed response
Summary measure: treatment difference of QM1114-DP and placebo in proportion of subjects that have at least “Improved” from baseline.		

Note that intercurrent events is defined as events occurring after treatment initiation that affect either the interpretation or the existence of measurements associated with the clinical question of interest.

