9.1.5 Inferential Statistical Analyses

The primary efficacy endpoint will be a responder rate based on the subject GAIS at Month 1. A responder is defined as a subject who responds at least “Improved” on the GAIS at maximum frown. The null hypothesis of no relationship between treatment and responder rate will be tested against the alternative hypothesis that there is a relationship between treatment and responder rate. The responder rates of the QM1114-DP and placebo will be compared using a Cochran-Mantel-Haenszel test, stratified by site, at 5% significance level (2-sided) based on the ITT population. Missing Month 1 GAIS data will be imputed with ‘No Change’. For consistency across strata (site), the Breslow-Day test will be used to assess the homogeneity of the odds ratios across all sites. Depending on the number of sites, pooling of sites may be needed.

For the primary efficacy endpoint, consistency of the results will be analyzed using Cochran-Mantel-Haenszel test stratified by gender, baseline ILA, prior use of botulinum toxin, and Fitzpatrick skin type, respectively.

[figure not shown]
All other efficacy and safety endpoints will be analyzed descriptively as appropriate.

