1.4 Efficacy endpoints

For all endpoints using responder rate, the responder rate is defined as $\frac{m}{n} \times 100$ where m is the number of responder subjects and n is the total number of subjects in the ITT population.

For all endpoints using proportion, the proportion will be calculated as $\frac{m}{n} \times 100$ where m is the number of subjects reporting the specified values on each question of the specified efficacy assessment at each visit, and n is the total number of subjects in the ITT population.

Percent of subjects in each response category will be calculated as $\frac{m}{n} \times 100$ where m is the number of subjects in each response category and n is the number of subjects

The definition of n will change based on the population used in the output.

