2.4.2 Handling of missing data

In general, the number of subjects with missing values will be summarized and reported as appropriate in all outputs. The primary analysis will be performed using the result of 'No Change' for any missing Month 1 GAIS assessment as the primary imputation method.

In addition, to further evaluate the impact of missing data on the primary endpoint, additional sensitivity analyses will be performed:

1. The primary analysis will be repeated using multiple imputation (MI) based on the ITT population
2. The primary analysis will be repeated using Observed Cases (OC) based on the ITT population (i.e., no imputation will be done)

The secondary efficacy analyses, exploratory analyses and safety analyses will be performed using OC. If deemed necessary, any analyses may be repeated using OC, 'No Change' imputation, baseline observation carried forward (BOCF), or MI as appropriate. Calculations for the FACE-Q and FLTSQ will follow the methods specified in the manuals for the handling of the data.

Missing data for Month 1 GAIS responses will be imputed using the following steps:

1. The imputation using MI will assume the Missing Completely at Random (MCAR) missing data assumption. Regardless of the actual pattern of missing data, the Markov Chain Monte Carlo (MCMC) method of the MI procedure from the SAS® system will first be used to create a monotonic pattern of missing data. The minimum values for imputed variables will be set to 0, in order to force PROC MI to redraw another value for imputation when an intended imputed value is less than the 0. The maximum value for imputed variables will be

set to 6, in order to force PROC MI to redraw another value for imputation when an intended imputed value is greater than 6. Imputed values will be rounded to the nearest integer. The seed number to be used will be the number 110196.

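### SAP 2.4.4 gives the primary estimand a completer denominator that contradicts its own 'No Change' rule, and SAP 1.4 gives observed-cases rates an all-ITT denominator

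*SAP*

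**What the plan says.** **Primary endpoint.** SAP 2.4.4 gives the estimand twice, in its opening sentence and in the endpoint row of its table. Both divide responders by those with a Month 1 GAIS; the sentence reads "divided by the number of subjects that completed the GAIS at Month 1, in all randomized subjects (ITT population". In the same table a missing Month 1 observation is intercurrent event 1, with the handling "Impute using the result of" 'No Change'. SAP 2.4.3 states "The primary efficacy endpoint will be based on the ITT population where missing Month 1 GAIS data will be imputed with" 'No Change', and Protocol 9.1.5 has the same rule: "Missing Month 1 GAIS data will be imputed with" 'No Change'. SAP 2.4.2 calls this the primary imputation method and lists multiple imputation and OC as sensitivity analyses.

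**Secondary endpoints.** SAP 1.4 defines the rate for all responder-rate endpoints as m/n × 100, "where m is the number of responder subjects and n is the total number of subjects in the ITT population". It gives a parallel rule for proportions, and closes by saying that n varies with the population used for the output. SAP 2.4.2 says: "The secondary efficacy analyses, exploratory analyses and safety analyses will be performed using OC". SAP 2.4.5 and Protocol 9.1.2.4 agree, and the secondary estimand table in SAP 2.4.5.1 leaves missing responses missing.

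**The concern.** An estimand states what the trial estimates, and the primary analysis should estimate it. Here the estimand's denominator leaves out the very subjects whom its own missing-data rule keeps in. It describes a quantity conditional on a post-randomisation event (completing the Month 1 GAIS), while the analysis estimates one over all ITT subjects.

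For the secondary GAIS rates the mismatch runs the other way. The data rule is OC, but the general formula divides by all ITT subjects. A table labelled OC and built on that formula would treat every missing visit as a non-response.

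What is at stake is the meaning and size of the reported rates and of their difference. Month 1 is exposed twice, because it is both the primary time point and one of the visits of the secondary GAIS endpoint (SAP 1.4.2). SAP 2.4.3 plans figures of the responder rates by visit, and SAP 2.4.5.3 plans a graph of rates over time. Month 1 could therefore appear with two values and no stated reason.

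**Working it through.** The plan gives no figure for this point, so there is none to reproduce first. The check sets the rules side by side and then works out how far apart they can be.

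**Inputs**
- 90 active and 30 placebo subjects (Protocol 5.1 and 9.2).
- Responder rates and missing fractions: assumptions. The sample-size assumptions in Protocol 9.2.1 to 9.2.3 are blacked out in the public copy, which is not a fault of the plan.

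**Step 1: the rules side by side**

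| Output | Rule | Denominator |
|---|---|---|
| Primary, SAP 2.4.4 definition | completers of the Month 1 GAIS | observed only |
| Primary, SAP 2.4.4 handling of missing data | 'No Change' | all ITT |
| Primary, SAP 2.4.2, SAP 2.4.3, Protocol 9.1.5 | ITT, 'No Change' | all ITT |
| Secondary, SAP 1.4 | general formula | all ITT |
| Secondary, SAP 2.4.2, 2.4.5, 2.4.5.1, Protocol 9.1.2.4 | OC | observed only |

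For each endpoint, one statement disagrees with the rest.

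**Step 2: formula.** In an arm with N subjects, missing fraction x and r observed responders:
- completer rate p = r / [N(1 − x)]
- ITT 'No Change' rate = r / N = p(1 − x)

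An imputed 'No Change' is never a response, so r is the same in both. It follows that the OC sensitivity rate, if computed with the n of SAP 1.4, would also be r / N and would simply repeat the 'No Change' rate.

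**Step 3: difference, equal missingness.** Assume p = 0.90 and 0.10. The completer difference is 80 points. The ITT difference is 0.80 × (1 − x):
- x = 5%: 76 points
- x = 10%: 72 points
- x = 15%: 68 points

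**Step 4: whole subjects**, at about 90% versus 10% among completers

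| Missing (active/placebo) | Completers | ITT 'No Change' |
|---|---|---|
| 0/0 | 81/90 − 3/30 = 80.0 | 80.0 |
| 2/1 | 79/88 − 3/29 = 79.4 | 79/90 − 3/30 = 77.8 |
| 5/2 | 76/85 − 3/28 = 78.7 | 76/90 − 3/30 = 74.4 |
| 9/3 | 73/81 − 3/27 = 79.0 | 73/90 − 3/30 = 71.1 |

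At 9/3 missing, the Wald 95% intervals are 65.5 to 92.5 (completers) and 57.7 to 84.6 (ITT). With an assumed 80% versus 20% and the same 9/3 missing, the differences are 61.7 and 55.6 points.

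**Step 5: direction.** Let pA and pP be the completer rates on active and placebo, and xA and xP the missing fractions. The ITT difference minus the completer difference is pP·xP − pA·xA. It is positive when pP·xP exceeds pA·xA. With 90% versus 10%, 1% missing on active and 15% on placebo, the ITT difference is 0.90 × 0.99 − 0.10 × 0.85 = 0.891 − 0.085 = 80.6 points, against 80.0 for completers.

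**Step 6: a late secondary visit.** Assume 20% missing on active and 36 responders. OC gives 36/72 = 50.0%; the formula in SAP 1.4 gives 36/90 = 40.0%.

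**The case against.** The strongest reply is that the analysis itself is clear. SAP 2.4.2, SAP 2.4.3, the subgroup repeats in SAP 2.4.4.2 and Protocol 9.1.5 all say ITT with 'No Change', and the handling row in 2.4.4 says so too. This stands. A reader might infer that the primary p-value or headline estimate depends on which sentence the programmer follows. The documents do not support that: the test, the rates, the difference and their intervals are specified together in 2.4.3 under one rule.

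For the secondary rates, the specific instructions are consistent and only the general formula in 1.4 differs. The closing sentence of 1.4 might be thought to settle it. It does not: it ties n to the population, the SAP has three populations (ITT, PP, Safety), and OC is a data rule applied within ITT. It remains true that these endpoints are descriptive and that no test turns on them.

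A reader might also suppose that missing visits would be hidden. SAP 2.4.2 already plans to report the number with missing values in the outputs, so the denominator would be wrong for OC but the missing count need not be concealed.

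Finally, the size is assumed. The COVID-19 provisions (Protocol 1.3, SAP 2.1.1) speak of cancelling only visits not needed for the primary endpoint, so the readable text gives no reason to expect heavy loss at Month 1.

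**Conclusion.** Wrong as written, and should be fixed. The primary estimand contradicts both its own handling of missing data and the analysis meant to estimate it. SAP 1.4 conflicts with the OC rule for the secondary endpoints. The confirmatory test is not affected.

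The discrepancy is zero if no GAIS data are missing. Under the assumed 90% versus 10% it is 4, 8 or 12 points in the difference at 5, 10 or 15% missing in both arms. These response and missing rates are illustrations, not document figures.

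It is tempting to add that the completer wording is always the more favourable. That holds for each arm's rate, which can only fall when missing subjects are added as non-responders. It does not hold in general for the difference, as Step 5 shows, although the reversal there needs placebo missingness more than nine times that on active.

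**What to change.** 1. **SAP 2.4.4, sentence and endpoint row.** Replace the completer denominator with all subjects in the ITT population, a missing Month 1 GAIS being counted as 'No Change' and so as a non-responder.
2. **SAP 1.4.** Keep n = total ITT for outputs that use 'No Change'. For every OC output, both responder rates and proportions, set n to the ITT subjects with a non-missing assessment at that visit.
3. **Labels.** Wherever a Month 1 responder rate appears in a table or figure, say whether it is the 'No Change' or the OC rate. Even after the first two edits Month 1 is legitimately reported under both rules, so the label is needed.

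The cost is a few sentences in the SAP, best made before unblinding so that the denominator is not settled with results in view. No test, sample size or study procedure changes. The headline rate may be slightly lower than the completer wording would give.
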